Assessment of a Fruit and Vegetable Prescription Program for Children

Trial #: NCT04767282

Study Protocol and Analysis Plan

Submitted: 11/06/2020

Background

The 2020-2025 Dietary Guidelines for Americans state that children and adolescents should consume fruits and vegetables regularly to support healthy development and prevent chronic disease. The US Department of Agriculture recommends a minimum daily intake of 1.5 cups of fruit and 1.5 cups of vegetables for females ages 9-13 years and 1.5 cups of fruit and 2 cups of vegetables for males ages 9-13 years.^{1,2} These recommendations often are unfulfilled, especially within low-income households.³⁻⁸ While most young people across the US struggle to attain even the minimum daily recommendations related to fruit and vegetable consumption,^{7,8} ultra-processed foods now comprise the majority of total energy intake among US youths 2-19 years.⁹ Increased adiposity related to shifts in diet and exercise have prompted public health action to encourage intake of fresh or minimally processed food among children and adolescents.¹⁰

Eating patterns during childhood and adolescence are important to long-term diet and health¹¹⁻¹³ and play a key role in the development of diet-related chronic health conditions.¹³⁻¹⁹ To support healthy food choices while also addressing food access challenges, some health care clinics have introduced fruit and vegetable prescription programs.²⁰⁻²³ The programs differ in design and scope, yet most include health provider-issued prescriptions that patients can exchange, without charge, for fresh produce at local farmers' markets, mobile markets, or food stores. While programs are increasingly available across the country, most target adults with chronic health conditions, offering fruit and vegetable prescriptions as a disease-management strategy.²²⁻²⁵ Few studies have examined whether, and to what degree, exposure to pediatric fruit and vegetable prescription programs influences the diet and health of youth.^{26,27} With childhood and adolescence representing a critical period of development when many are establishing lifelong dietary behaviors,¹¹⁻¹³ these programs are likely to have meaningful health implications.

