Demographically similar pediatric patient groups with varying levels of exposure to the FVPP at baseline will be compared: high exposure (>24 months), moderate exposure (12-24 months), and no previous exposure. Children with no previous exposure will be introduced to the FVPP, and researchers will track changes in dietary intake, food security, and weight status over two years. The specific aims of the study are to (1) compare baseline dietary intake, food security, and weight status between pediatric patients with varying levels of exposure to the FVPP; (2) measure changes in diet, food security, and weight status before and after never-before-exposed children are introduced to the FVPP; and (3) compare mean 12- and 24-month follow-up measures of dietary intake, food security, and weight status in the initial no exposure group to baseline measures in the high exposure group. A central expectation is that greater exposure to this FVPP will promote intake of fruits and vegetables, better food security, and lower rates of childhood obesity.

The current study, in design and approach, is grounded in the theoretical framework of Bandura's Social Cognitive Theory (SCT). SCT explains behavior using a three-stage, dynamic model linking personal factors, environmental factors, and behavior.^{30,31} This study's SCT framework involves collaborations with partnering physicians and local agricultural leaders to support environmental change and social learning. Since children's dietary intake is generally guided by their parents, critically important environmental factors, such as access to fruits and vegetables as well as caregiver modeling of the healthy behaviors, are of particular importance.^{32,33} Consistent with SCT, we also posit that self-efficacy is central to behavior change. Accordingly, self-efficacy for consuming fruits and vegetables, which refers to one's judgment over one's capability to enact the behavior, is important to change dietary behavior.³⁴ By grounding the study with the theoretical framework of SCT, we suggest that pediatrician issuance of a prescription for fruits and vegetables to every child at each office visit will promote food access and self-efficacy to consume healthy foods. Furthermore, pediatrician messaging to children and caregivers will influence health-promoting behaviors linked to increased consumption of fruits and vegetables.

Study Design

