This study will include a cross-sectional analysis of data from a consecutive sample of caregiver-child dyads with varying levels of exposure to a fruit and vegetable prescription program (FVPP) that provides one \$15 prescription for fresh produce to every child during pediatric office visits. Considering the importance of dietary patterns during childhood on long-term diet and health¹¹⁻¹³ alongside evidence that indicates adolescence is the specific period when food insecurity has the greatest potential to negatively impact the diet,³⁵ data collection and analyses will focus specifically on children and adolescents ages 8-16 years. A total of 700 caregiver-child dyads (one caregiver and one child per household) will be enrolled in the study, with approximately 200 dyads enrolled at clinic 1 (high exposure); 200 dyads enrolled at clinic 2 (moderate exposure), and 300 dyads enrolled at clinic 3 (no previous exposure to the FVPP). A description of the clinics is provided with our explanation of the 'Setting' for this study.

Dyad enrollment will be based on exposure to the FVPP as defined by caregiver-reported and clinic-verified length of time that the participating child has been a patient at one of three partnering clinics. Accordingly, we expect dyads to cluster based on pediatric clinics as follows: clinic 1 (high exposure), clinic 2 (moderate exposure), and clinic 3 (no previous exposure). A sample of approximately 200 pediatric patients newly exposed to the FVPP at clinic 3 will be followed for a period of two years as part of a non-controlled longitudinal intervention trial that will examine changes in dietary patterns, food security, and weight status over time.

Setting

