Flint, Michigan, is a low-income urban city where an approximate 60% of children live in poverty, and full-service grocery stores located inside the city are limited.³⁶ The city lacks resources and nutritional options, like many low-income urban cities in the US. As a result, many children consume insufficient nutrient-dense foods and excessive poor-quality, calorie-dense foods.²⁰ Local stores in Flint tend to offer lower-quality foods and fewer healthy foods than offered in higher-income neighborhoods.^{28,37-39} Along with long-lasting issues related to food access and affordability coupled with recovery from a drinking water crisis,⁴⁰ the SARS-CoV-2 coronavirus pandemic has disproportionately affected Flint and surrounding Genesee County. Confirmed COVID-19 case prevalence has consistently placed the county in the top ranks (#5) among 83 Michigan counties. In ordinary times, with constrained wealth, and many families in poverty, under- or unemployed, Flint faces extraordinary health challenges. The pandemic has compounded these ordinary challenges, with results that include more hungry children and increased food insecurity.

The current study will occur at three clinics in Flint serving demographically similar patient populations.

- Clinic 1 is a university-affiliated pediatric clinic that introduced Michigan's first pediatric fruit and vegetable prescription program. The program began as a pilot in February 2016. After several program iterations and refinements, all patients currently receive one \$15 prescription for fresh fruits and vegetables at every office visit. Pediatricians at clinic 1 have distributed approximately 40,000 prescriptions since the FVPP was introduced.
- Clinic 2 is one of the largest private-practice pediatric clinics in Flint, serving over 3,000 young patients. The FVPP was introduced at clinic 2 in August 2018 as part of a grant to assess the feasibility and preliminary effectiveness of the FVPP at a second clinic site.²⁶ Clinic 2 was selected for this expansion because of the clinic size, demographics of the patient population which closely match clinic 1, and use of an electronic medical record (EMR) system that is identical to clinic 1 (allowing easy tracking of monthly prescription distribution rates). Clinic 2 has distributed over 15,000 prescriptions since August 2018.

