- Clinic 3 is the largest pediatric clinic in Genesee County, with Flint as its urban center. Expansion of the FVPP to clinic 3 will substantially increase program reach among vulnerable children and families living in Flint. Last year, clinic 3 had over 12,000 pediatric visits. It has a comparable patient population to clinics 1 and 2, serving only children in need who are residents of Genesee County.

Participants and recruitment

A sample of 250 caregiver-child dyads presenting at clinic 1, 250 caregiver-child dyads at clinic 2, and 350 caregiver-child dyads at clinic 3 will be assessed for eligibility, with 700 total dyads enrolled (anticipated 10-15% not meeting eligibility and 10% refusal based on a previous study). To control for confounders, we will adopt a balancing strategy that consists of recruiting in the study children who have approximately the same age, sex, and race across the three clinical settings. These children will not be balanced according to variables pertaining directly to the exposures (e.g., duration of FVPP exposure).

With target samples of 200, 200, and 300 caregiver-child dyads enrolled in clinic 1 - high exposure, clinic 2 - moderate exposure, and clinic 3 - no previous exposure, respectively, we have well above 90% power to jointly detect modest relative differences in the baseline mean intake of vegetables of 20% from clinic 2 to clinic 3 and 38% from clinic 1 to clinic 3. This calculation assumes an underdispersed Poisson model with a dispersion parameter of 0.82, derived using previously published data on the mean intake of vegetables of 0.72 cup and a standard deviation of 0.77 cup in the settings with no prior FVPP exposure.²⁰ Likewise, with 300 caregiver-child dyads enrolled in clinic 3, we have well above 90% power to detect a modest temporal improvement in the mean intake of vegetables of 25% over 12 months (0.72 cup at baseline versus 0.90 cup at 12-month follow-up). This calculation assumes a correlated Poisson model for underdispersed count data with timepoint dispersion parameter of 0.82, and a modest temporal correlation of 0.2. Increasing values of the temporal correlation greatly improves the statistical power. Finally, estimation of FVPP effects will specify two-tailed tests with alpha set at the 0.05 level.

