Inclusion criteria for all participants include a restriction to children aged between 8 and 16 years at enrollment; the caregiver and child must speak English. An estimated 2% of the Flint population cannot speak English. A legal guardian must be present at enrollment and must sign an informed consent document; each child must assent to participation. Inclusion criteria for clinic 1 (high exposure) will include participation in the FVPP for over 24 months. Inclusion criteria for clinic 2 participants (moderate exposure) will include participation in the FVPP for 12 to 24 months. Inclusion criteria for clinic 3 participants (no exposure) will include no previous exposure to the FVPP. Potential participants at clinic 3 will be excluded if the household includes a sibling who already enrolled in the research study or if there has been movement of the patient from one clinic to another clinic (<3% of patients).

Fruit and Vegetable Prescription Program (FVPP)

Fruit and vegetable prescriptions, analogous to medical prescriptions, are electronically prescribed by pediatricians and given to patients. They are intended to promote a healthy food environment within the home.⁴¹ For our study, eligible vendors comprise the downtown Flint Farmers' Market (FFM) and Flint Fresh, a mobile market and food hub that offers locally grown, home-delivered, fresh produce boxes. Vendors accept the prescriptions (\$15 each) as if they were gift certificates or vouchers for any fresh fruits or vegetables. In partnership with FFM and Flint Fresh, prescription redemption rates are recorded and tracked. Over time, the redemption of prescriptions has been increasing (from under 30% when the program was initiated to its current redemption rate of approximately 50%).

Clinics 1 and 2 have developed an efficient and reliable method to record and track prescription distribution rates. Fruit and vegetable prescriptions are built using the Epic electronic medical record (EMR) system, to order and print each prescription, and to track individual and aggregate monthly distribution rates. Key personnel on the current study will train pediatricians and staff at clinic 3 regarding EMR procedures to order, print, and track prescriptions through their EMR system, eClinicalWorks (eCW). The study protocol will capture monthly reports that cover topics such as the number of patients seen in the clinic and prescriptions distributed.

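### Each exposure level is recruited at one clinic only, so between-group programme effects rest on an unstated no-clinic-effect assumption, and clinic 2's 12-24 month window leaves launch-era patients in no group

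*Combined protocol and SAP*

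**What the plan says.** Study aims and hypotheses sets three groups: "high exposure (>24 months), moderate exposure (12-24 months), and no previous exposure". Study Design bases enrolment on the caregiver-reported and "clinic-verified length of time that the participating child has been a patient at one of three partnering clinics", and adds that "we expect dyads to cluster based on pediatric clinics as follows", one level per clinic. Table 1 likewise measures exposure as months as a patient at a participating office, alongside the number of prescriptions received.

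Participants and recruitment turns that expectation into a rule. Clinic 1 children need more than 24 months and clinic 3 children none. For clinic 2: "Inclusion criteria for clinic 2 participants (moderate exposure) will include participation in the FVPP for 12 to 24 months". The same section plans to assess "250 caregiver-child dyads at clinic 2" to enrol 200, with "anticipated 10-15% not meeting eligibility and 10% refusal based on a previous study".

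Setting gives the launch: "The FVPP was introduced at clinic 2 in August 2018". The title block reads "Submitted: 11/06/2020". No enrolment start date is given.

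The Statistical analysis plan acknowledges that the design is not randomized. It plans regression adjustment, then a generalized propensity score from a multinomial logistic model with child and caregiver covariates. It describes the resulting estimate of the average programme effect as unbiased.

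**The concern.** Two problems arise from the same eligibility rule.

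First, with one exposure level per clinic, any lasting difference between clinics in patients, neighbourhood, staff or counselling appears in the data exactly as an exposure effect would. Clinic 1 is university-affiliated and clinic 2 is a private practice, so such differences are plausible. Matching on age, sex and race, and adjusting for child and caregiver variables, cannot separate the two. A reader who takes the claim of unbiasedness at face value would credit the programme with whatever distinguishes the clinics.

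Second, the 12-24 month window looks out of step with the calendar. A child attending clinic 2 since launch passed 24 months in August 2020. The rule names the over-24-month category only for clinic 1, so that child belongs nowhere, and the moderate group narrows to more recent joiners. Neither the expected clustering by clinic nor the ineligibility allowance appears to account for this.

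**Working it through.** **1. Can exposure and clinic be separated?** Code the design with an intercept, two exposure indicators and two clinic indicators. Under the eligibility rule the clinic indicators duplicate the exposure indicators: 5 columns, rank 3. The propensity model has the same limit. If clinic is added, it predicts the category with probability 0 or 1 and no overlap remains. If it is left out, the estimate assumes no clinic effect given the covariates.

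**2. What a clinic difference would do (assumed sizes).** The documents give no clinic difference. The plan's variance inputs are mean 0.72 cup, SD 0.77 and dispersion 0.82 (check: 0.77²/0.72 = 0.823). For 200 v 300 children at equal means:

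SE = √(0.82 × 0.72 × (1/200 + 1/300)) = 0.070 cup.

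With no programme effect and this SE, a two-sided 0.05 test rejects as follows:
- assumed clinic shift 0.05 cup: 11.0%
- assumed clinic shift 0.10 cup: 29.7%

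A 600-replicate simulation used 200/200/300 children, SD 0.77, two mildly imbalanced covariates, propensity weighting and zero programme effect. With assumed shifts of +0.10 cup (clinic 1) and +0.05 cup (clinic 2), the weighted estimates were +0.108 (high v none) and +0.055 (moderate v none). With no shifts they were +0.001 and -0.005. Weighting passes the clinic difference through as a programme effect.

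**3. Clinic 2 dates, counting time as a patient since launch.**
- August 2018 + 24 months = August 2020.
- August 2018 to November 2020 = 27 months (26-27, depending on the day in August).
- In November 2020 the window admits children who joined between November 2018 and November 2019.
- A day-first reading of the submission date (11 June 2020) gives 21-22 months, but the 24-month limit is still passed for any enrolment after August 2020. The reference list has access dates of 14 November 2021, when the figure is 38-39 months.

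A clinic 1 child with 12-24 months also fits no group.

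**4. Screening allowance at clinic 2.** The plan's own figures give 250 × 0.85 × 0.90 = 191 to 250 × 0.90 × 0.90 = 203, consistent with a target of about 200. Reaching 200 needs 200/(250 × 0.90) = 89% of assessed children to be eligible. The share inside the window is not in the documents. Assumed shares of 50%, 25% and 10% would give 250 × share × 0.90 = 112.5, 56.3 and 22.5 enrolled.

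**5. Power if the moderate group changes.** The log-mean variance is 0.82/(n × mean), with a two-sided Wald test at 0.05 and none = 0.72 with n = 300. The 20% and 38% differences can be read two ways.

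| Reading | Moderate, high means | Moderate v none at n = 200 / 100 / 50 | Joint 2-df test, 200 / 50 moderate |
|---|---|---|---|
| Multiply 0.72 | 0.864, 0.994 | 50% / 35% / 23% | 91.3% / 91.1% |
| 0.72/0.80, 0.72/0.62 | 0.900, 1.161 | 68% / 50% / 32% | 99.95% / 99.95% |

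The plan's joint power above 90% is reproduced on either reading. The joint test would not reveal a loss in the moderate contrast.

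**6. Would mixing bands within clinics help?** The simulation was repeated with clinic 1 and 2 children equally likely to be in either band. The clinic-adjusted high v moderate estimate was -0.001 cup (SE 0.077). The unadjusted contrasts with none stayed biased by about +0.077 and +0.076, because only clinic 3 supplies that group.

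**The case against.** The design is disclosed as non-randomized, the clinics are described as demographically similar, and the propensity score is offered as an alternative that mitigates baseline differences. Every propensity estimate rests on an untestable condition. This stands as far as it goes, and it is why the defect is an unstated assumption rather than an invalid method. A reader might infer that the propensity analysis is worthless or must be biased. The documents do not show that: if clinic has no effect given the covariates, the estimate is sound. They give no grounds for assuming so, and unbiasedness is claimed without the condition.

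On the window, participation could be dated from a first prescription rather than from joining the clinic. An established clinic 2 patient first prescribed between November 2018 and November 2019 would then qualify in November 2020. The eligibility wording allows this. Study Design and Table 1 point to time as a patient, so the start of exposure needs one definition.

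A reader might also infer that the moderate group will miss 200. The documents do not support that. The in-window share is unknown, the target is approximate, 250 assessed need not be a ceiling, and clinic 2 serves over 3,000 patients. Nor does the goal of learning about duration collapse: Aim 2 follows clinic 3 children at 12 and 24 months within one clinic. The prescription count in Table 1 would also permit within-clinic dose analyses, but the plan specifies none.

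**Conclusion.** The confounding is complete by construction for Aim 1 and for Aim 3's comparison with the high-exposure group, and it does not depend on any date. The average programme effect across these groups is not identified without assuming that clinic has no effect on outcome given the child and caregiver covariates. The claim of unbiasedness should not stand. The size of any bias cannot be known from the documents; the 11% and 30% rejection rates illustrate assumed shifts. Aim 2 is not affected by this confounding.

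The window problem holds on the time-as-a-patient definition and for enrolment after August 2020. Launch-era clinic 2 children then fit no group, which sits poorly with the expected clustering and the 10-15% ineligibility allowance. How many children this touches is not stated, so it is an inconsistency to reconcile and not a demonstrated shortfall.

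**What to change.** 1. In the Statistical analysis plan, describe the propensity result as an estimate adjusted for measured child and caregiver covariates. State the no-clinic-effect assumption. State that contrasts between exposure groups are confounded with clinic and will be reported as associations.
2. Reconcile Study Design, the inclusion criteria and Table 1 with one chart-verified start of exposure: the later of programme launch at the clinic and the child joining it. Say whether clinic 1's pilot period counts. Assign clinic 1 and clinic 2 children to 12-24 or over 24 months by those months, not by clinic. If the moderate group changes, restate expected group sizes and Aim 1 power under a declared reading of the 20% and 38% differences, including the moderate v none contrast.
3. Tabulate months of exposure by clinic. Add a sensitivity analysis in clinics 1 and 2 with a clinic term and months of exposure, reported as an estimate with a confidence interval. State that without overlapping months it identifies only within-clinic slopes under an assumed functional form, which is the case if enrolment followed the present rule. State also that it does not repair contrasts with clinic 3.

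The cost is an eligibility amendment, one extra model and a corrected sentence. No new data are needed, since months already come from chart review. The downsides are a weaker causal claim and possibly a smaller moderate group, partly offset by clinic 1 children at 12-24 months. The precision of the clinics 1-2 model cannot be computed from the documents.

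### Clinics 1 and 2 are selected on time as a patient and clinic 3 is not, so the Aim 1 exposure contrast is mixed with length of registration

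*Combined protocol and SAP*

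**What the plan says.** Under Study Design, enrolment is by exposure, "defined by caregiver-reported and clinic-verified length of time that the participating child has been a patient at one of three partnering clinics". Table 1 likewise lists months as a patient at a participating office, from chart review, as an exposure measure.

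Participants and recruitment then sets three different rules:

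- Clinic 1: "Inclusion criteria for clinic 1 (high exposure) will include participation in the FVPP for over 24 months".
- Clinic 2: "Inclusion criteria for clinic 2 participants (moderate exposure) will include participation in the FVPP for 12 to 24 months".
- Clinic 3: "Inclusion criteria for clinic 3 participants (no exposure) will include no previous exposure to the FVPP".

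Clinic 3 children are also excluded if a sibling is already enrolled or "if there has been movement of the patient from one clinic to another clinic (<3% of patients"). Neither exclusion sets a minimum or maximum time as a patient.

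The same section controls confounding at recruitment by "recruiting in the study children who have approximately the same age, sex, and race across the three clinical settings", and adds: "These children will not be balanced according to variables pertaining directly to the exposures (e.g., duration of FVPP exposure").

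Length of registration is not among the baseline covariates in the covariate section, nor among the adjustment variables named under Comparison of baseline measures based on FVPP exposure. The propensity model in the Statistical analysis plan refers only to child-level and caregiver-level covariates in general.

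**The concern.** Once exposure is measured by time as a patient, the clinic 1 and clinic 2 criteria also select on registration length. Clinic 1 is restricted to longer-registered children, clinic 2 to a 12-month band, and clinic 3 is unrestricted. A first-visit child can enter clinic 3 but not clinic 1 or 2. A child registered for five years can enter clinic 3 but, on the Study Design definition, not clinic 2.

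If diet, food security or weight varies with how long a family has been attached to one clinic, a difference would appear between the groups in Aim 1 even if the FVPP did nothing. This is separate from differences between the clinics themselves. Those cannot be separated from exposure when exposure is expected to cluster by clinic. Registration length can be, because clinic 3 may hold unexposed children at every registration length.

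**Working it through.** **The three rules side by side, on the Study Design definition**

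| Group | Months as a patient | FVPP |
|---|---|---|
| Clinic 1 | more than 24 | yes |
| Clinic 2 | 12 to 24 | yes |
| Clinic 3 | any | none |

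The Setting section dates the FVPP at clinic 2 from August 2018, and the plan was submitted on 11/06/2020. Read as month/day/year, that is about 27 months. A clinic 2 child already registered at launch would be past the 24-month cap, so clinic 2 would then hold children who registered after launch.

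**The plan's own figures, as background**

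Inputs from Participants and recruitment: mean 0.72 cup, SD 0.77 cup, differences of 20% and 38%, groups of 200, 200 and 300, two-sided alpha 0.05.

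- Dispersion = 0.77² / 0.72 = 0.823, against the stated 0.82.
- Planned differences: 0.20 × 0.72 = 0.144 cup (clinic 2 v 3) and 0.38 × 0.72 = 0.2736 cup (clinic 1 v 3).
- Joint power from a 2-df Wald test in a quasi-Poisson model: 91.3% on the log scale, 90.8% on the identity scale. The plan gives only a phrase (well above 90%), so there is no exact figure to match.

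**How a registration effect would enter Aim 1 if the FVPP had no effect**

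Let d be the mean vegetable intake of longer-registered minus recently registered children. The documents give neither d nor the share of recent registrants, so both are assumed, and d could have either sign.

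1. *Intake differs at 24 months.* Let f be the share of clinic 3 registered 24 months or less. Clinic 1 minus clinic 3 = f × d. Clinic 2 minus clinic 3 = −(1 − f) × d. With f = 0.20 and d = 0.2 cup these are +0.04 and −0.16 cup, which are opposite in sign.
2. *Only the first 12 months differ.* Let g be the share of clinic 3 registered under 12 months. Both contrasts shift by g × d, in the same direction:

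| g | d (cup) | Shift (cup) | Share of 0.144 | Share of 0.2736 | Joint false-positive rate |
|---|---|---|---|---|---|
| 10% | 0.1 | 0.01 | 7% | 4% | 5.2% |
| 20% | 0.2 | 0.04 | 28% | 15% | 8.8% |
| 30% | 0.3 | 0.09 | 63% | 33% | 27% |

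For food security, an assumed 20-point difference with 10-25% recent registrants moves the clinic 3 prevalence by 0.10 × 20 = 2 to 0.25 × 20 = 5 points. None of these figures allows for covariate adjustment.

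**Precision of a matched comparison**

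With equal variances and n clinic 3 children kept, the standard error ratio is √(1/n + 1/200) / √(1/300 + 1/200).

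- Clinic 1 v 3, 10% excluded: n = 270, ratio 1.022.
- Clinic 1 v 3, 25% excluded: n = 225, ratio 1.065.
- Clinic 2 v 3, 50% of clinic 3 in the 12-24 month band (assumed): n = 150, ratio 1.18.
- Clinic 2 v 3, 25% in the band (assumed): n = 75, ratio 1.48.

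Pairwise power = Φ(ln(m/0.72) / √(0.82/(200m) + 0.82/(0.72n)) − 1.96), where m is the exposed-clinic mean.

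- Clinic 1 v 3 (m = 0.9936): 95.1% with 300, 94.1% with 270, 91.9% with 225.
- Clinic 2 v 3 (m = 0.864): 50.5% with 300, 37.5% with 150, 25.2% with 75.

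**The case against.** **The plan leaves room to adjust.** The list of adjustment variables is open-ended, the Statistical analysis plan promises a search for further confounders, and a generalized propensity score is planned. Income, caregiver education and food-assistance participation may carry part of any registration effect. This stands in part: it would be wrong to infer that the plan forbids adjustment. But registration length is never named, and entering it as an ordinary covariate would not work well. At clinics 1 and 2 it is the exposure measure, and their ranges do not overlap.

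**The clinic-movement exclusion may remove new arrivals.** It may remove some, if it covers transfers from any practice. The text does not say so, and it would not clearly reach children new to the area or to care.

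**The criteria speak of FVPP participation, not registration.** True of the wording. They become registration rules through the Study Design definition and Table 1.

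**Nothing shows that recent registrants differ.** This stands. A reader might infer that clinic 3 is loaded with less settled families and that the FVPP will look better than it is. The documents do not support that: they give neither the share nor the characteristics of recent registrants. The 24-month cap at clinic 2 means clinic 3 may be the longer-registered group in that contrast.

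**Aim 3.** A reader might extend the concern to Aim 3. There, clinic 3 children are measured 12 and 24 months after enrolment, so those retained have gained that much registration time and the gap with clinic 1 largely closes.

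**Conclusion.** The point holds for Aim 1 as a difference between groups that the eligibility rules create and that no named step in the plan removes. It rests on the Study Design definition of exposure as time as a patient. The size and direction of any bias are unknown. Under the assumed inputs it runs from negligible to a substantial share of the planned differences, and the two contrasts may be biased in opposite directions. It does not show that Aim 1 will favour the FVPP. Aim 2 compares each child with itself and is not affected by this imbalance between clinics. It is a worthwhile, inexpensive improvement, not a fatal flaw.

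**What to change.** 1. Record chart-verified months registered at the clinic for clinic 3 children as well. Study Design already refers to clinic-verified time at all three clinics, but Table 1 ties the measure to participating offices, so this should be made explicit.
2. Pre-specify for Aim 1 a tenure-matched analysis beside the full-sample analysis: clinic 1 against clinic 3 children registered more than 24 months, and clinic 2 against clinic 3 children registered 12 to 24 months. The upper limit matters; a comparator of at least 12 months would include longer-registered children than clinic 2 admits.
3. Because the two contrasts use different clinic 3 subsets, report them as separate pairwise comparisons and keep the three-group joint test for the full sample.
4. Keep all clinic 3 children in Aim 2, and set no pre-enrolment registration minimum for Aim 3. Requiring more than 24 months before enrolment would put clinic 3 children beyond 24 + 24 = 48 months at the last visit, against more than 24 at clinic 1.

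The cost is one chart field and one analysis-set rule. The matched clinic 1 v 3 standard error is about 2-6.5% wider under the assumed 10-25% exclusion. The clinic 2 v 3 analysis could lose much more if few clinic 3 children fall in the 12-24 month band, and should then be read as supportive only. The full-sample analysis keeps its planned numbers.
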